11.3.1. Assessment of severity and causality

All SAEs must be assessed for severity by the PI(s) or by those members of the research team specifically authorised by the Principal Investigator(s) to assess SAEs, as documented in the site delegation log. Assessments of severity will be made according to the following conventions:

- Mild: An event that is easily tolerated by the patient, causing minimal discomfort and not interfering with every day activities
- Moderate: An event that is sufficiently discomforting to interfere with normal everyday activities
- Severe: An event that prevents normal everyday activities

The term 'severe', used to describe the intensity of an event or reaction, should not be confused with the term 'serious' which is a regulatory definition. For example, a headache may be severe but not serious, while a minor stroke may be serious but is not severe.

¹ Life-threatening in the definition of a serious adverse event or serious adverse reaction refers to an event in which the subject was at risk of death at the time of event; it does not refer to an event which hypothetically might have caused death if it were more severe.²⁰

An assessment of the causal relationship between an SAE and trial participation will be made according to the standardised guidance given in Table 2 below:

Table 2: Definitions of Causality

Relationship	Description
Unrelated	There is no evidence of any causal relationship
Unlikely	There is little evidence to suggest there is a causal relationship (e.g. The event did not occur within a reasonable time after administration of the trial treatment/procedure). There is another reasonable explanation for the event (e.g. The participant's clinical condition, other concomitant treatment).
Possible	There is some evidence to suggest a causal relationship (e.g. Because the event occurs within a reasonable time after administration of the trial treatment/procedure). However, the influence of other factors may have contributed to the event (e.g. The participant's clinical condition, other concomitant treatments).
Probable	There is evidence to suggest a causal relationship and the influence of other factors is unlikely.
Definitely	There is clear evidence to suggest a causal relationship and other possible contributing factors can be ruled out.

11.3.2. Assessment of expectedness

SAEs deemed to be possibly, probably or definitely related to trial participation will be classified as SARs. In such cases, the PI or authorised delegate will make a judgement on whether the event is expected or unexpected. The assessment of expectedness will be made with reference to the known risks listed in section 10.3. An event will be classed as unexpected if it is not listed in protocol section 10.3.

11.4. Processing Serious Adverse Event report forms

On receipt of a completed SAE form, PenCTU will assign a unique SAE number and confirm receipt of the event to the reporting site and to the study Sponsor. Staff from the reporting site will file the receipt confirmation and the original SAE report form in the relevant participants CRF. Any further correspondence relating to the same event (e.g. data query forms) must also be filed with the original form.

If incomplete information is available at the time of reporting, all appropriate information relating to the SAE will be forwarded to PenCTU as soon as possible. All serious adverse events will be followed up until resolution.

11.4.1. Onward reporting

SAEs will be reported on a periodic basis to the Sponsor, CI and Trial Steering Committee in order to maintain sufficient oversight of trial safety.

SAEs deemed related to the trial procedures and which are unexpected are subject to expedited reporting; they will be notified to the Research Ethics Committee (REC) within 15 days for a non-life threatening event and within 7 days for a life-threatening event. Such events will be reported to the Trial Steering Committee on an ongoing basis.

12. STATISTICS AND DATA ANALYSIS

12.1. Sample Size Calculation

The study is powered to detect a 10-point difference in ankle score since patient and public involvement indicated that walking without aids/getting back to work were the most important issues. A change from support with a stick/crutch to no support and a change to getting back to normal work/activities of daily life from simpler or part-time work are both associated with a 10-point change on the Olerud and Molander¹⁴ subjective scale (primary outcome).

An estimate of standard deviation of the ankle score six weeks post-surgery was derived from an audit of 18 patients having plaster casts at Poole Hospital. This figure of 21.9 is very similar in magnitude to those reported in the Cochrane review¹³. Based on an unpaired t-test with two groups of equal size, assuming 90% power, a two-sided 0.05 significance level, a standard deviation of 21.9 and a mean difference of 10 points between the plaster and boot groups, a total sample size of 204 (102 in each group) is required²¹. The study will over-recruit by 20%²² to allow for non-responders, or missing data, not to contribute data to the main analysis. However it is anticipated that the true percentage will be reduced by offering flexible methods of completion; either online, post or by phone. As the study progresses, the percentage with missing primary outcome data will be monitored and discussed at regular trial management group meetings and reductions/increases in over-recruitment will be made accordingly so that the target of 204 with completed data is met.

The study will aim to recruit 246 patients in total (123 in each group) over a 2 year recruitment period.

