1. STUDY SYNOPSIS

Study title	Does early mobilisation after Ankle fracture surgery enhance Recovery ? A pragmatic multi-centre randomised controlled Trial with qualitative component and health economic analysis comparing the use of plaster versus removable support boot (ART).
Short study title:	The Ankle Fracture Recovery Trial (ART)
Study design	This study is designed as a pragmatic multi-centre randomised controlled trial with qualitative component and health economic evaluation comparing plaster cast and support boots as methods of post-operative ankle fracture management.
Study participants	
Inclusion Criteria
 
 • Received surgery for fixation of unstable ankle fracture • Provision of informed consent to participate 
Exclusion criteria
 
 • Under 16 year olds (skeletally immature). • Poor skin condition at operation site. • Serious concomitant disease (e.g. stroke, osteoporosis, arthritis). • Diabetic neuropathy/other sensory neuropathy (lack of sensation). • Non-ambulatory prior to injury. • Active leg ulceration. • Patients who are unable to understand the study information or unable to complete the outcome questionnaires. • Surgeon concerned about quality of fixation/integrity of wound. • Fracture requiring further stabilisation in/around the ankle (e.g. syndesmosis). • Open ankle fracture (bone broken through skin). • Participant is a participant in other concurrent interventional research which may over-burden the participant or confound data collection. • Concomitant injuries which will have a confounding effect on rehabilitation in the opinion of the investigator.
Number of participants	276 patients in total (138 in each treatment group).
Follow-up duration	Patients will be followed up in clinic at 4 weeks post-baseline (6 weeks post-operatively) and via questionnaires), at 5 weeks post-baseline (7 weeks post-operatively) and 10 weeks post-baseline (12 weeks post-operatively). Qualitative telephone interviews with up to 20 participants will take place after the 10-week follow up.

Planned study period	48 months (37 month recruitment period)
Study aim	To evaluate the relative effectiveness and cost-effectiveness of two methods of post-operative ankle fracture management (plaster versus removable support boot allowing range of movement) and to provide evidence-based recommendations for best care in clinical practice.

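### The protocol gives two recruitment targets and two recruitment periods (276 over 37 months in the synopsis, 246 over 2 years in section 12.1), and only 246 is derived

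*Protocol*

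**What the plan says.** The synopsis (protocol section 1) gives the number of participants as "276 patients in total (138 in each treatment group" and the planned study period as "48 months (37 month recruitment period".

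Section 12.1, the only place where the size is justified, proceeds as follows:

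- It works from a t-test ("Based on an unpaired t-test with two groups of equal size", "assuming 90% power", "a two-sided 0.05 significance level", "a mean difference of 10 points between the plaster and boot groups") with a standard deviation of 21.9, and arrives at 204 patients, 102 per arm.
- It then adds an allowance for non-response and missing data: "The study will over-recruit by 20" per cent.
- It expects the actual percentage to be lower, because participants may complete questionnaires online, by post or by phone.
- It says missing primary outcome data will be monitored, and over-recruitment raised or lowered, so that 204 patients provide complete data.
- It closes with "The study will aim to recruit 246 patients in total (123 in each group) over a 2 year recruitment period".

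**The concern.** The total, the number per arm and the recruitment period all differ between two parts of the same current document. Each pair is coherent in itself (2 × 138 = 276; 2 × 123 = 246), so this does not look like a misprint or a reading fault. Neither place is a summary of changes, and no other section explains the difference.

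The planned size and the end of recruitment are commitments on which sites, the ethics committee and the Trial Steering Committee (section 13.5 gives it oversight of recruitment) rely, and against which the final report will be read. As written, a reader cannot tell whether recruitment is planned to end at 246 or 276, or at 24 or 37 months. Stopping at 246 falls 30 short of the synopsis. Going on to 276 randomises 30 more than 12.1 aims for, with no stated reason.

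The size of the allowance matters in this trial. Under section 12.2, primary outcome questionnaires completed outside the 3 to 10 day window count as missing, and the main effectiveness analyses use no imputation. Late and absent responses therefore both reduce the analysed number, and over-recruitment is what protects the 204.

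**Working it through.** **Inputs** (all from section 12.1 unless noted): difference 10; SD 21.9; two-sided alpha 0.05; power 90%; equal arms; allowance 20%; targets 246 (12.1) and 276 (synopsis).

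**1. Reproduce the 204.** The standardised difference is 10 / 21.9 = 0.457.

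- Normal approximation: n per arm = 2 × (1.960 + 1.282)² × (21.9 / 10)² = 100.8, so 101 per arm.
- Exact noncentral t: n per arm = 101.76, so 102 per arm and 204 in total, with power 90.1%.

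The protocol's 204 is correct for the t-test it names.

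**2. Reproduce the 246.** Over-recruiting by 20% means multiplying by 1.2: 102 × 1.2 = 122.4, rounded up to 123 per arm, so 246. This matches exactly.

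**3. Try to reach 276.**

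| Reading of the 20% | Formula | Total |
|---|---|---|
| 20% added to the completers | 102 × 1.2 = 122.4, so 123 per arm | 246 |
| 20% of recruits lost | 204 / 0.8 = 255, or 128 per arm | 255 (256 with equal arms) |

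Neither gives 276. The ratio 276 / 204 = 1.353, so 276 is 35% above the completers needed.

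**4. Loss that each target can absorb while keeping 204.**

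- 246: 1 − 204 / 246 = 17.1%
- 276: 1 − 204 / 276 = 26.1%

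**5. Power if 20% of recruits were lost** (exact t-test, an illustrative loss rate).

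| Recruited | Completers | Per arm | Power |
|---|---|---|---|
| 246 | 246 × 0.8 = 196.8 | 98.4 | 89.0% |
| 276 | 276 × 0.8 = 220.8 | 110.4 | 92.2% |

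**6. Size of the contradiction.** 276 − 246 = 30 patients; 138 − 123 = 15 per arm; 37 − 24 = 13 months.

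**The case against.** The strongest defence is that the binding target is 204 completers, not a number recruited. Section 12.1 expressly lets over-recruitment move so that 204 is reached, and 276 could be such an increase. The effect size, SD, alpha, power and completer target are the same under either headline figure, so no analysis changes. This stands as a limit on the consequences. It does not remove the contradiction: the protocol nowhere says that 276 arose under that rule, and 12.1 still presents 246 over 2 years as the aim.

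Three stronger readings are tempting, and the document does not support them.

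- A reader might infer that 246 is an arithmetic error that costs the trial its 90% power. The text speaks of over-recruiting by 20%, and 246 does exactly that. Treating the 20% as a loss rate is plausible, since the following sentence speaks of a percentage that should turn out lower, but it is an interpretation. Even then the shortfall is about 7 completers and one point of power, which the adjustment rule would make up. The SD itself rests on an audit of 18 patients, so one point is well inside the uncertainty of the calculation.
- A reader might infer that 276 was planned for 26% missing data. That percentage is only back-calculated from 276, and the protocol states no such assumption.
- A reader might infer that, at 276, section 12.1 no longer describes the trial. Only its closing sentence conflicts with the synopsis, and the derivation of 204 still applies.

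**Conclusion.** The contradiction is real and needs correcting. The two statements of the target differ by 30 patients (15 per arm) and the two recruitment periods by 13 months, with nothing to reconcile them. Only 246 is justified in the text. This conclusion rests on the wording alone and needs no assumption about loss.

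The inflation is a minor, separate note. It applies only if the 20% is meant as an expected proportion lost, in which case 246 covers about 17% and gives about 89% power at 20% loss. That is not a material failure to deliver 90% power. It is no reason to call the trial underpowered, particularly given the commitment to recruit until 204 complete.

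**What to change.** - State one target (total and per arm) and one recruitment period, identically in the synopsis and in section 12.1.
- If 276 over 37 months is current, replace the last sentence of 12.1 and give the sponsor's actual missing-data assumption or other reason for the increase. It can be added as a fact that 276 keeps 204 completers up to about 26% missing, but that figure should not be entered as the rationale unless it was.
- If 246 over 2 years is current, correct the synopsis.
- In either case, say whether the 20% is an addition to the completers or an expected loss. If it is a loss, the formula is 204 / (1 − proportion lost), which at 20% gives 255 (256 with equal arms).

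The cost is a change of wording, with ethics committee and local NHS approval of the amendment as appropriate (section 13.1). It requires no patients beyond a target the protocol already states, and no change to the analysis.

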12.2. Description of statistical methods

A detailed Statistical Analysis Plan will be developed and signed off by the Trial Steering Committee before any analyses commence. The anonymised data will be analysed by 'intention to treat' (i.e. patients will be analysed in the treatment arm they were randomised to, even if they received something else, or swapped treatments). The analysis and initial write-up will be blinded to the treatment groups and will report according to the Consolidated Standards of Reporting Trials²³⁻²⁴, including a participant flow chart. No imputation methods for missing data will be used for the main effectiveness analyses.

12.2.1. Baseline descriptives:

Baseline descriptive data on demographics (gender, age, marital status, whether living alone, highest educational level, employment status, driving status), fracture characteristics (fracture classification, pattern, complexity), BMI, Olerud and Molander ankle score pre-injury, and EQ-5D will be presented overall and for both groups separately. This will help with (a) assessment of external validity of the trial, and (b) to see whether the 2 groups were comparable at baseline (no significance tests will be conducted). The Olerud and Molander scale includes a question on activity compared to before injury. This would make this question confusing to complete at baseline, and so for baseline only this question has been dropped and

all participants will be given the maximum score of 20 for this question (i.e. the score for work and activities same as before injury).

12.2.2. Primary outcome:

The primary outcome is the Olerud and Molander¹⁴ ankle score (measured out of 100) five weeks post-baseline. Questionnaires that were not completed in the 3-10 day time window will be treated as missing data.

Multiple regression including study site, age and fracture complexity as a factor will be used to compare mean ankle score at five weeks post-baseline between the plaster and boot groups.

Instead of implementing stratification of age and fracture complexity at randomisation (which in any case could be problematic if there is a large number of strata with a relatively small sample size), the potential issue of imbalance in age and fracture complexity between the two arms of the trial will be addressed by adjusting (stratifying) for the covariates of age (as a continuous variable) and fracture complexity in the analysis. Thus the proposed analysis of the primary outcome, for example, will use multiple regression and, in addition to treatment arm, include the pre-specified variables of study site, age and fracture complexity.

Two groups are proposed regarding fracture complexity: Simple fibular fracture and comminuted fracture. If the fibular fracture has a single fracture line with two discrete fragments only, it comprises a 'simple' fracture. If the fibula has more than one fracture line and therefore more than two discrete fragments that require accurate reduction to achieve stability, it comprises a comminuted fracture. The pattern and complexity of the fracture can influence the choice of hardware used by the surgeon to achieve stability. Simple fractures are fixed with unlocked plates whereas complex fractures can require more sophisticated and expensive locked plates.

The pre-baseline measure is collected retrospectively and so has not been included in the primary analysis. By ten weeks post-baseline, it is anticipated that both groups will be similar on the primary outcome, and so this has not been included in an overall repeated measures type analysis. The five week post-baseline data collection period is the critical period, as this is when it is anticipated that the group who had boots will have a greater level of function^{3,6}.

Some additional analyses (including sensitivity analyses) on primary outcome will also be conducted:

(a) It is acknowledged that some participants (in either group) will leave the 4 week appointment with a plaster cast or boot, and so will complete the scale whilst still wearing the plaster/ boot. In a supplementary sensitivity analysis these participants will be excluded from the analysis to see if the results change.

(b) Pre-injury Olerud and Molander scale will be included as a covariate.

(c) Whether or not the patient had a medial malleolar fracture will be included as a covariate

(d) Any baseline variables that appear, by chance, to differ between the groups will be added in as covariates.

(e) The effectiveness of the intervention may vary across different subgroups (strata) of patients (e.g. age and fracture complexity). Therefore for each outcome

supplementary statistical analyses are proposed in which it is tested whether there is a statistical interaction between age and treatment arm and between fracture complexity and treatment arm. It is however acknowledged that statistical power will be reduced for these significance tests and they will be considered to be exploratory. Age will be grouped as: under 65 years of age at the time of fracture and 65 + years.

(f) The main analysis will use an “intention to treat” approach. As a supplementary analysis two sets of “per protocol” analyses will also be conducted. In the first of these, patients will be analysed according to the method (boot or plaster) that they actually wore. If patients crossed over from one to the other during the 4 week period they will be excluded from the per protocol analysis. If patients didn’t wear the boot/plaster for the full 4 weeks they will be excluded. In the second analysis participants will additionally be excluded if they didn’t perform the exercises recommended. Thus if they performed the exercises less than once per day they will be excluded

(g) Data on primary outcome completed outside of the 3-10 day window will be included in the analysis

(h) The robustness of the results to missing data will be assessed by repeating the analysis incorporating the imputed values that will be derived as part of the economic analysis (see section 12.4)

The study will also compare the ten week Olerud and Molander Ankle score between groups to check whether any differences still remain at 10 weeks.

To see whether patients in both groups have returned to pre-injury levels of function we will calculate the mean difference (95% CI) between pre-injury and 10 week values for each group, and the proportion of patients whose score is worse by 10 points or more. These statistics will also be compared between groups.

12.2.3. Secondary outcomes:

The profiles from the patients’ answers to the EQ-5D-5L will be weighted using the EuroQol’s published United Kingdom societal utility tariffs to produce a composite, utility based quality of life score and EuroQol has piloted the 5L valuation scores²⁵. If final scores are not available by the end of the trial, the crosswalk developed by EuroQol from the three level scores will be used. Quality Adjusted Life Years will then be created from the four time point utility scores assuming a linear change between the time points and using the area under the curve approach. Incremental QALY gains between arms will then be estimated using regression analysis adjusted for baseline utility and site, age and fracture complexity variables.

Multiple regression will be used to investigate differences between the two groups in the other continuous outcomes measured at four weeks post-baseline (e.g. degrees of range of movement (dorsiflexion, plantarflexion, inversion, eversion), circumferential swelling and 10 weeks (e.g. return to daily activities on 0-10 scale). Complications in the two groups (presence and severity), healing status (displaced / undisplaced and evidence of post-operative fracture healing (yes/no)), employment status at 10 weeks, driving status and weight bearing status will be investigated using logistic regression (binomial or multinomial depending on the number of categories), again taking study site, age and fracture complexity into account. Survival analysis will be used to investigate the time from randomisation to starting to drive again. Supplementary analysis (b) to (e) as described for the primary outcome will also be conducted for secondary outcomes.)

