9.4.2. End of 4-week follow up visit procedures

A member of the research team will ensure the following before the patient leaves the hospital:

- A copy of the 5-week follow-up questionnaires (and a freepost envelope) will be given to participants. They will be instructed on how to complete the questionnaire using their preferred option (online, phone or post). The importance of completing the questionnaire within 3-10 days will be emphasised. Participants will be encouraged to complete the questionnaire online. If they would prefer not to use the online method, they will be encouraged to complete over the phone. Those participants, who state that they are unable to complete the questionnaire online or by telephone, will use postal completion. Participants who are completing questionnaires online will be emailed to access this approximately 3 days after their 4 week clinic appointment. Participants who have opted for telephone completion will be telephoned approximately 5 days after their 4 week clinic appointment. Participants will be encouraged to have the paper version of the questionnaire by their side during the phone call.
- The patient has their Patient Diary and is aware that they will be receiving questionnaires in approximately 6 weeks' time by post/email and that they may be contacted in the event that the questionnaires are not returned so as to prompt for return or to complete the questionnaire over the telephone.

The research team will also ensure that the patient's continuing participation in the trial is appropriately recorded in the hospital records in accordance with local practice.

Completed questionnaires and CRF pages will be sent to PenCTU using FREEPOST envelopes.

9.5. 5-week follow-up questionnaire completion

The 5-week follow-up requires participants to complete a questionnaire comprising the following:

- Olerud and Molander (1984) ankle score (see section 7.1)
- EQ-5D-5L (see section 7.2)

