The aim is to collect data on primary outcome and EQ-5D-5L at 5 days after the participants 4 week clinic visit. Most participants will have had their plaster / boot removed at the 4 week appointment. It is thought that any benefits resulting from use of the boot would be apparent at this time point. The time window for a valid response will be defined as 3-10 days after the 4 week appointment. The method of data collection has been designed to minimise the risk of missing data. Too much missing data may have a negative impact on the statistical analysis and

interpretation of results (e.g. less precision and possibility of bias). For ease of communication this follow-up will be referred to as the 5 week follow-up.

PenCTU staff will monitor receipt of questionnaires and will issue reminders to patients if the questionnaire has not been returned. If a questionnaire has not been received within 8 days from the week 4 visit, attempts will be made to contact the participant by telephone and the option of completing the questionnaire by telephone will be available.

9.6. 10-week follow-up (12 weeks post-surgery)

9.6.1. 10-week follow-up questionnaire completion

The 10-week follow-up requires participants to complete a questionnaire comprising the following:

- Olerud and Molander (1984) ankle score (see section 7.1)
- EQ-5D-5L (see section 7.2)
- Resource use questionnaire (see section 7.4)
- Return to activities (see section 7.2)

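### A 5-week paper form posted back before day 3 is missing for the main analysis but still switches off reminders, so an in-window primary outcome can go uncollected on the postal route

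*Protocol*

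**What the plan says.** **Validity rule.** Section 9.5 states: "The time window for a valid response will be defined as 3-10 days after the 4 week appointment". Section 12.2.2 applies it to the primary outcome: "Questionnaires that were not completed in the 3-10 day time window will be treated as missing data". Both rules turn on when the form was completed. Section 12.2 rules out imputation in the main effectiveness analyses.

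**Chasing rule.** Also in section 9.5: "PenCTU staff will monitor receipt of questionnaires and will issue reminders to patients if the questionnaire has not been returned", and "If a questionnaire has not been received within 8 days from the week 4 visit, attempts will be made to contact the participant by telephone". Both triggers turn on whether a form has arrived.

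**Issue of the form.** The section on end-of-visit procedures at 4 weeks states: "A copy of the 5-week follow-up questionnaires (and a freepost envelope) will be given to participants". On timing it adds: "The importance of completing the questionnaire within 3-10 days will be emphasised". Online completers "will be emailed to access this approximately 3 days after their 4 week clinic appointment", and telephone completers are called at about day 5. Online is encouraged first and telephone second; post is for those who say they can manage neither.

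**Backstops.** Section 12.1 has the percentage of missing primary outcomes monitored and over-recruitment changed so that 204 completed outcomes are reached. Supplementary analysis (g) in section 12.2.2 brings out-of-window scores back in, and analysis (h) uses imputed values.

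**The concern.** One questionnaire is governed by two rules with different criteria. A form completed too early fails the validity rule but satisfies the chasing rule. The participant has cooperated, can be reached and could still answer inside the window, but nothing in section 9.5 prompts anyone to ask again.

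The floor at day 3 has a purpose. Section 7.1 wants participants to have had some days out of the cast or boot before function is scored. A score from days 0 to 2 does not measure that state, and no later analysis can supply the measurement that was not taken.

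At stake is the completeness of the primary outcome. Section 9.5 says the collection method was designed to protect it, and section 7.4 keeps resource-use questions out of the 5-week contact partly for the same reason.

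**Working it through.** The check is mainly one of logic; arithmetic only bounds the size.

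**1. Follow one early form through the rules.** Day 0 is the 4-week visit.

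| Step | Rule | Result for a postal form completed on days 0 to 2 |
|---|---|---|
| Form in hand | End of 4-week visit procedures | Yes, from day 0 |
| Valid? | 9.5 and 12.2.2: completed on days 3 to 10 | No; missing in the main analysis |
| Reminder? | 9.5: only if not returned | No, once it has arrived |
| Call at day 8? | 9.5: only if not received | No, if it has arrived by then |
| Date check or repeat request? | Not stated | None |

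At completion, 10 − 2 = 8 to 10 − 0 = 10 days remain before the window closes. Transit uses some of this. A form arriving on day 3 leaves 10 − 3 = 7 days; one arriving on day 5 leaves 5.

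**2. Compare the three routes.**
- Online: a link at about day 3, whether or not paper has arrived.
- Telephone: a call at about day 5, whether or not paper has arrived.
- Post: no scheduled contact in the window; only the receipt-based triggers apply.

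The gap is therefore essentially postal.

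**3. Compare the 10-week form.** In section 9.6.1 the window starts when the questionnaire is issued, so no reply can precede it and a receipt trigger works. The 5-week form is issued before its window opens, so the same kind of trigger does not.

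**4. Reproduce the plan's sample size.** Inputs from section 12.1: difference 10, SD 21.9, two-sided 0.05, 90% power, equal groups.
- Standardised difference: 10 / 21.9 = 0.457.
- Unpaired t-test (noncentral t): n = 101.76, so 102 per group and 204 in total, as stated. Power at 102 per group is 90.1%.
- Over-recruitment: 102 × 1.2 = 122.4, so 123 per group and 246 in total, as stated in section 12.1.

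**5. Slack for missing outcomes before 204 is breached.**
- With 246 recruited (section 12.1): 1 − 204/246 = 17.1%.
- With 276 recruited (synopsis): 1 − 204/276 = 26.1%.

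The two targets disagree, which is a separate matter. Early forms use part of whichever slack applies.

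**6. Illustrative cost.** The documents give neither the postal share nor the early-completion rate. Assume 2%, 5% or 10% of otherwise evaluable participants are voided; the upper end looks high for a last-resort mode. To hold 204 completers from the section 12.1 base, divide 246 by (1 − share):

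| Assumed share voided | Recruits needed | Extra recruits | Completers if nothing is adjusted | Power if nothing is adjusted |
|---|---|---|---|---|
| 2% | 246/0.98 ≈ 251 | about 5 | 204 × 0.98 ≈ 200 | 89.5% |
| 5% | 246/0.95 ≈ 259 | about 13 | 204 × 0.95 ≈ 194 | 88.5% |
| 10% | 246/0.90 ≈ 273 | about 27 | 204 × 0.90 ≈ 184 | 86.8% |

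The last two columns apply only if the section 12.1 adjustment is not made.

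**The case against.** The strongest reply is that this is a narrow operational matter which the plan largely covers.

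- **Reach.** Two of the three modes have a scheduled contact at about day 3 or day 5, and post is the last choice. This stands. A reader might infer that any early form, whatever the mode, ends contact; the text does not support that.
- **Power.** The target of 204 is defined after missing data, and section 12.1 commits to changing recruitment to reach it. This stands. A reader might subtract voided forms from 204 and report power below 90%, but that ignores the stated adjustment. For example, 276 recruits with 20% ordinary missingness and a further 8% voided still leave 276 × 0.80 × 0.92 ≈ 203.
- **Analysis.** Analysis (g) restores early scores and (h) uses imputed values, so the loss is confined to the main analysis. This stands in part: both probe the effect of the exclusions, but neither provides a score taken in the window.
- **Bias.** One might argue that early completers are a selected group, so the result is biased. That is possible, but nothing in the documents shows it or its direction.
- **Unseen procedures.** Section 9.5 defines a valid response beside the triggers, so the trials unit might in practice chase until it holds one, and a work instruction or the form itself may deal with dates. That an early form counts as received is an inference from plain wording. The protocol points to no procedure that closes the gap.

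**Conclusion.** The point holds for the postal route. The protocol judges a 5-week form by its completion date but stops chasing on its arrival, and it issues the form three days before the window opens. Read literally, an early postal form ends follow-up and the in-window primary outcome is not collected, although there is time to obtain it.

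The size is unknown and probably small. It rests on the shares using post and completing before day 3, neither of which is given. If the section 12.1 monitoring works, the price is some avoidable missing primary outcomes and a few extra recruits: about 5 if 2% are voided and about 13 if 5% are, both assumed. Neither a loss of power nor bias in the treatment comparison is demonstrated.

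This is not something to leave to the statistical analysis plan, which cannot recover a measurement that was never requested. Severity: minor, a cheap improvement.

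**What to change.** In section 9.5:

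1. Base both the reminders and the day-8 telephone call on whether a questionnaire completed on days 3 to 10 has been received, in place of whether any questionnaire has been returned or received.
2. Have PenCTU check the completion date at receipt. If it is before day 3 or missing, ask the participant promptly to repeat the score by telephone, online or post within the window. Keep the early score for analysis (g).
3. Print the participant's first and last valid completion dates on the paper form handed out at the 4-week visit, so that the window is not taken for a simple deadline.

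The cost is a short change to section 9.5, a date check at receipt and a few additional contacts. The downside is that a few participants answer a short questionnaire twice. The window, the primary analysis and the sample size stay as they are.
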